9.6 Data Management

Data will be collected on paper-based CRFs at site by the site staff. No data will be directly captured on to the CRF.

The database design will be set-up by Syne Qua Non within a fully validated clinical database data management system, Syne-clin II¹, in accordance with Syne Qua Non's standard operating procedures. All data will be entered onto Syne Qua Non Ltd computer database by a member of the data management section and then verified by repeat data entry by a further section member. Standard Query Language edit checks (as defined in the Study Validation Plan) will be used to

¹ Syne-clin II is a fully validated MS Access®/SAS based system with validated ODBC links to ODBC compliant database management systems e.g. Oracle.

Validation of computer systems at SQN are performed in compliance with the principles of the United Kingdom Statutory Instrument 2004 No. 1031 The Medicines for Human Use (Clinical Trials) Regulations and subsequent amendments, the International Conference on Harmonisation Good Clinical Practice guidelines and the United States Food and Drug Administration Rule 21 CFR Part 11, Electronic Records; Electronic Signatures – Scope and Application.

Details of the validation of Syne-clin II are presented in the table below; the current validation certificate is available as a stand-alone document in Annex I.

Name of Software	Date software was Implemented	Version of the software/tool that is being used	Licensing Agreement with Software Provider		Hosting the System
Data Management - Syne-clin II in house	1997	5.08/08 Mar 2016	N/A	N/A	In house closed system

validate the data post entry. Consistency reviews will be performed by data managers directly within Syne-clin II using a series of data validation scripts based on the study validation plan.

9.7 Data Analysis

A statistical analysis plan (SAP) will be developed by a qualified statistician and analysis will be performed according to this document. The SAP will specifically include details of how all: Analysis Populations, Demographic and Baseline Characteristics, Completion and Discontinuation information, Medication details and All Analyses (rate of incorrect dosing, rate of previous opioid usage immediately prior to Ayendi, time of dosing, product strength and number of sprays, indication, ED practice setting, administrator, concomitant medication, and adverse events) will be classified and described. The SAP will be reviewed and approved prior to database lock.

The sample size chosen for the study is considered appropriate based on previous experience. This is an observational study of patients receiving prescribed Ayendi in a UK Hospital Emergency Department. The sample size will have sufficient power to estimate both the rate of incorrect dosing and use in association with other opioids.

Changes in the conduct of the study or planned analyses will be reported in the corresponding section of the study report.

9.7.1 Analyses

Reporting of the data will be of a descriptive nature and presented using appropriate summary statistics or frequency distributions stratified by age group and weight bands. Unless otherwise stated these tabulations will be supported by data listings.

Age and weight stratifications will be undertaken at the end of the study on the complete dataset. These will be based on the SmPC patient groups in terms of age and weight, as specified in the combined SmPC posologies as well as those patients who are outside the authorised age groups.

The presentation of the age and weight strata will be based on the presentation of summary statistics (e.g. n, mean, SD, %CV, median, minimum, maximum) or frequency distributions (n%). The summaries will be presented if the number of available data points is at least 5. If the number of data points is 4 or less then the summary statistics will only present the sample size (n) and the minimum and maximum values. No percentages less than 1% will be presented for frequency counts but the available sample size (n) will still be presented. As no formal statistical testing is planned there is no requirement to pool stratum comprising small samples of patients. This approach will be fully documented in the SAP.

Summaries will include all patients for whom appropriate informed consent was obtained to allow collection of their data. AEs will be coded according to the current version of MedDRA (version to be identified in study report).

Concomitant medications will be listed and coded according to Medication class (WHO ATC Level 2) Standardised medication name (WHO ATC Level 4).

Treatment emergent adverse events (TEAEs) will be determined and only these will be included in the statistical analysis report. Details of the criteria of classifying an AE as a TEAE will be provided in the Statistical Analysis Plan (SAP).

The incidence of adverse events will be summarised by system organ class, preferred term and maximum severity. Adverse events will also be summarised by strongest relationship to Medicinal Product by event and system organ class. If a patient experiences an adverse event more than once, the event with the worst severity or at the most related to MP occurrence will be considered. Patients will be included only once at each level where they experienced one or more events.

A summary of the incidence of serious adverse events will be presented by event and system organ class.

9.7.2 Statistical analysis

Analysis Populations

Data will be presented for the Safety population, that is, it will include all patients for whom appropriate informed consent was obtained to allow collection of their data.

Data Analysis

Statistical analyses will be performed after all patient data have been collected, protocol deviations reviewed, populations have been agreed and the database has been locked.

Details of all analyses will be included in the SAP.

Continuous variables will be summarised using descriptive statistics; n, mean, standard deviation, median, minimum and maximum, while categorical variables will be summarised as the number (and percentage) of patients in each category.

Demographic data will be summarised overall and by weight in accordance with the approved posology categories, and otherwise, as appropriate.

Concomitant medications will be tabulated by weight group along with the current available WHO drug dictionary coding by primary term and generic drug name.

Safety analyses will be simply summarised.

Adverse events will be coded according to the current version of MedDRA.

Missing, Unused or Spurious Data

The handling of missing, unused and spurious data will be described in the SAP.

Deviations from the Planned Statistical Analyses

Any changes to the planned analysis (as described in the protocol and SAP) will be documented in the statistical and clinical study reports.

9.7.3 Quality Control

The database will include data storage tables, entry and edit screens, validation rules and programs, audit trails and tracking systems. For the Tables and Listing validation process, Syne Qua Non will double-programme all the tables and analysis datasets. The listings will be program reviewed by a second programmer. A statistician will perform a high level review of all the tables and listings and checked the output against the final statistical analysis plan (SAP).

9.8 Quality Assurance

An appropriate number of sites will be selected for audit by an independent auditor.

In order to check the compliance of the study regarding GCP, audits may be carried out by a quality assurance representative. The investigator will provide access to authorised persons during regulatory authority inspections or Sponsor audits.

9.8.1 Study Monitoring

Appropriately qualified and trained staff will be involved in this study. Staff at the investigational site will be instructed in the conduct of the study according to this protocol.

Sponsor personnel will monitor the site on a 4 to 8 weekly basis during the study recruitment phases to assure adherence to the protocol. During these visits, the CRFs and other study documentation will be checked for accuracy and completeness, and to permit 100% source data verification for 10% of transcribed records.

The investigator will agree to provide the monitor direct access to the patients' source data, which may exist in the form of hospital records, patient files and notes, and laboratory assessment reports and results.

9.8.2 Trial Documentation and Storage

The investigator/institution should maintain the trial documents in a comprehensive and centralised filing system that is suitable for inspection by representatives of the Sponsor and regulatory authorities. The investigator/institution should take measures to prevent accidental or premature destruction of these documents.

Essential documents as defined by ICH GCP include the signed protocol and any amendment(s), copies of the completed CRFs, signed informed consent forms from the parent(s)/legal guardians of all patients for whom consent was obtained, hospital records and other source documents, REC approvals and all related correspondence including approved documents, site delegation lists and curriculum vitae, study correspondence and a list of the patients' names and addresses.

The principal investigator must retain copies of all essential documents for the period specified by ICH GCP and by applicable regulatory requirements.

The principal investigator will inform the Sponsor of the storage location of the essential documents and must contact the Sponsor for approval before disposing of any of these documents.

It is the responsibility of the Sponsor to inform the investigator/institution as to when these documents no longer need to be retained. The Sponsor should be informed immediately by the investigator/institution of any change concerning archiving facilities.

Handling, processing, storage and destruction of data will be compliant with the Data Protection Act of 1998.

9.9 Limitations of the Research Methods

As this is an observation study of post authorisation drug utilisation, the sites included in this study are limited to EDs which have independently, without reference to this study, made the decision to use Ayendi.

In an effort to avoid bias, sites will be included that have a history of the use of nasal diamorphine as well as sites that have rarely or never administered it prior to purchasing Ayendi. Additionally, units that have a dedicated paediatric ED department as well as those that are part of the general adult ED will be included. Also, recruitment per site will be limited to a maximum of 60 patients (15% of the overall sample size) to ensure that the overall estimate is not too affected by one site. By use of these measures, and having a patient population of 400, bias will be reduced, and a representative position of the UK EDs should be obtained.

9.9.1 Consideration of potential bias introduced by the consent processes

It is well documented that consenters and non-consenters (including proxy consent) can differ, that getting consent can be challenging, but that full consent is generally expected in many areas of research. An observational study design where consent is not taken until after the patient receives Ayendi as part of routine clinical practice somewhat reduces the bias introduced by the consent process, thus capturing the true patient population. However, consent may be more or less likely depending on whether other opioids are given, or if incorrect dosing is used. In particular, if incorrect dosing has clinical consequences patients/parents/legal guardians may be less likely to consent and results could be biased downwards.

Therefore, the MHRA have requested a separate data extraction be conducted where investigators and their teams will extract, then anonymise, retrospective data from patient case notes without actively seeking consent.

The summary data from this retrospective data extraction will be used to provide validation for the results of the prospective study.

In order to collect a similar level of detail in the information from the two studies so as to ensure reasonable comparability between the data sets of a prospective and a retrospective study, no clinical data outside of what is routinely recorded in the ED records will be collected for the prospective study, DIA003.

A minimum of 5 sites will provide the retrospective, anonymised data on a number of additional patients who have been dosed with the product. Timing and number of patients will be agreed in advance on a site by site basis.

It is anticipated that sites in the retrospective data extraction will not have participated in the prospective study. However, due to the practicalities of obtaining retrospective data on a new medicine, sites from the prospective study may need to be included. The busy nature of an emergency department means there will have been patients at these sites who were treated with Ayendi but who were not approached to provide consent to participate in the prospective study.

However, if patients were approached for the prospective study and refused consent, their case notes will not be included in the retrospective data extraction.

The retrospective data extraction will likely begin towards the end of the prospective study due to the practicalities of obtaining retrospective data on a new medicine. Approval for this retrospective data extraction will be sought separately.

9.10 End of study

For administrative and safety reporting purposes the end of the study will be defined as after the last patient's hospital discharge. This provides for a single and conservative definition.

10. PROTECTION OF HUMAN SUBJECTS

The study will be planned, initiated, managed and reported with safeguards in place in order to comply with national and European Union requirements for ensuring the well-being and rights of participants in non-interventional post-authorisation safety studies. That is:

- The study will be initiated, managed and financed by Wockhardt voluntarily or pursuant to obligations imposed [by regulators] and which involve the collection of data on suspected adverse reactions from patients or healthcare professionals
- Payments to healthcare professionals for participating in study shall be restricted to the compensation for time and expenses incurred
- The MHRA may require Wockhardt to submit the protocol and the progress reports
- The protocol will be actively approved by the MHRA prior to study commencement
- Substantial Protocol amendments will be actively approved by the MHRA
- Wockhardt will send the final report to the MHRA within 12 months of the end of data collection
- Automatic, formal assessment and decision-making will be based on the results of the study
- Any new information which might influence the evaluation of the risk- benefit balance of the medicinal product shall be communicated from Wockhardt to the MHRA
- Wockhardt will update the product information, as appropriate following this process

This study will be conducted in accordance with the ethical principles that have their origin in the Declaration of Helsinki, and are consistent with ICH-GCP (effective as of 17-JAN-1997) and applicable regulatory requirements. Regulatory authorities will be notified and consulted as required prior to, during, and after the conduct of the study.

10.1 Informed consent

Before the data of a patient under the age of 18 years old can be included in the study, their parent(s)/legal guardian must give written informed consent to the data inclusion. Where applicable, the patient themselves will provide assent for the study (generally in patients over 7 years of age). Adult patients capable of consent must provide written informed consent to the inclusion of their data.

Patient information leaflets about this study will be provided which target specific age groups and levels of understanding in order to obtain patient assent for the study as well as for adult patient/parental/legal guardian consent.

10.2 Patient Confidentiality

The principal investigator must ensure that the patient's anonymity is maintained. On the CRFs or other documents submitted to the Sponsor, patients should not be identified by their names, but by their assigned identification number and initials only. If patient names are included on copies of documents submitted to the Sponsor, the names (except for the initials) must be obliterated and replaced with the assigned study patient numbers.

The principal investigator should keep a separate log of patient identification numbers, names, addresses, telephone numbers and hospital numbers (if applicable). Documents not for submission to the Sponsor, such as signed informed consent forms, should be maintained in strict confidence by the principal investigator in the study site file.

A screening log will be maintained for patients who have been approached to participate in the study and have refused consent or consented to participate in the study but for whatever reason, consent was subsequently withdrawn. This log will contain the following information:

- ▶ Patient study number
- ▶ Patient initials
- ▶ Reason for refusal/withdrawal of consent (if available)
- ▶ Other reason(s) for non-inclusion of data (if applicable)

CRF pages will not be completed for these patients.

The investigator shall permit authorised representatives of the Sponsor, regulatory authorities and IECs to review that portion of the patient's medical record that is directly related to the study. As part of the required content of informed consent, the patient must be informed that his/her records will be reviewed in this manner.

11. MANAGEMENT AND REPORTING OF ADVERSE EVENTS/ADVERSE REACTIONS

This is a non-interventional study based on secondary use of data and will be conducted in compliance with GVP Module VIII and VI, where appropriate. As such, and in accordance with GVP Module Section VIII.B.6.2 and GVP Module VI Section VI.C.1.2.1., expedited reporting of Serious Adverse Events is not required in this study.

Assessments of safety will be performed throughout the time that the patient is in the hospital according to standard ED practice. No further data will be collected regarding the patient once they have left the ED.

11.1 Adverse Events

11.1.1 Definition of Adverse Events

For the purposes of this study, AEs will be defined as any new diagnosis, any reason for referral to a consultant, any unexpected deterioration in a concurrent illness, any suspected adverse drug reaction, or any complaint which was considered to be of sufficient importance such that it should be recorded in the medical/nursing notes from the point of administration of Ayendi.

The principal investigator will assess the severity of all AEs according to routine practice at the hospital. The investigator will also assess the relationship of AEs to Ayendi using the criteria used during routine clinical practice.

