	
 ▶ Strength and dose administered ▶ Any issues with dosing as per the routine practice in the ED records. ▶ Adverse events that occur prior to discharge/transfer from the ED ▶ Serious Adverse Events that occur prior to discharge/transfer from the ED 
Study-specific information from the informed consent form and the study identification log includes the following:
 
 ▶ Unique subject identifier to identify site and subject number in study ▶ Administration setting ▶ Date of informed consent (subject assent, if applicable) ▶ Confirmation of adherence to inclusion criteria 
This is purely an observational study and no further information will be documented as part of the study. Information not recorded as part of routine clinical practice should not be included in the CRF, even when available – the CRF is not regarded as primary source data.
 
Safety Assessments:
 
Assessments of safety will be performed throughout the time that the patient is in the hospital according to standard ED practice.
 
No further data will be collected regarding the patient once they have left the ED.
 
Adverse event recording
 
Adverse events will be defined as any new diagnosis, any reason for referral to a consultant, any unexpected deterioration in a concurrent illness, any suspected adverse drug reaction, or any complaint which was considered to be of sufficient importance such that it should be recorded in the patient’s medical/nursing notes. These data will be transcribed onto the CRF.
 
Only AEs that are recorded in the patient’s hospital notes as part of routine clinical practice will be recorded in the CRF.
 
Adverse event reporting
 
This is a non-interventional study based on secondary use of data and will be conducted in compliance with GVP Module VIII and VI, where appropriate. As such and in accordance with GVP Module Section VIII.B.6.2 and GVP Module VI Section VI.C.1.2.1., expedited reporting of Serious Adverse Events is not required in this study.
 
All adverse events, including Serious Adverse Events, will be reported in the Clinical Study Report.

STUDY DURATION:
	
Data collection will be requested for the single visit to the ED.

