11.2.1 Definition of Serious Adverse Events (SAEs)

A **Serious Adverse Event** (SAE) is defined as one of the following:

- An event that causes the death of the patient.
- A life-threatening* event.
- An event causing hospitalisation** or prolongation of existing hospitalisation.
- An event causing persistent or significant disability or incapacity***.
- An event causing a congenital anomaly or birth defect in the offspring of a woman treated before or during pregnancy.
- Important medical events (i.e., not immediately life-threatening or do not result in death or hospitalisation but require urgent and intensive intervention to prevent one of the outcomes listed in the definition above, for example, intensive treatment at home or in an emergency room for bronchospasm or convulsion)

* The term ‘life-threatening’ refers to an event in which the patient was at risk of death at the time of event; it does not refer to an event that hypothetically might have caused death if it were more severe.

** A hospitalisation is defined as an overnight stay, including time spent in an emergency room, for an AE. A prolongation of existing hospitalisation is defined as an additional overnight stay. Elective surgery is not classified as an SAE. For the purposes of this study, presentation in an Emergency Department or hospitalisation for the presenting injury will not be considered an SAE unless there is a prolongation to the anticipated duration of hospitalisation for an injury of that nature. Any other unanticipated outcome of the presenting injury that meets the definition of a serious adverse event should be reported as an SAE

*** The term ‘persistent or significant disability or incapacity’ refers to an event that results in a substantial or permanent disruption of patient’s ability to carry out normal life functions.

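### The AE definition lacks the presenting-injury exemption that the SAE definition has, so the overall AE percentage can be inflated, and unevenly across sites.

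*Protocol*

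**What the plan says.** Protocol section 11.1.1 gives the working definition: "AEs will be defined as any new diagnosis, any reason for referral to a consultant". It goes on to unexpected worsening of a concurrent illness, suspected drug reactions, and complaints important enough to be "recorded in the medical/nursing notes from the point of administration of Ayendi". The abstract, under adverse event recording, repeats the list ("Adverse events will be defined as any new diagnosis, any reason for referral to a consultant") but leaves out the closing reference to the administration of Ayendi.

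Section 11.2.1, in its footnote on hospitalisation, says that "presentation in an Emergency Department or hospitalisation for the presenting injury will not be considered an SAE" unless the stay runs longer than expected for an injury of that kind. No matching sentence appears in 11.1.1 or in the abstract's AE definition.

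Three further provisions bear on what is finally reported:

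- Section 9.7.1: "Treatment emergent adverse events (TEAEs) will be determined and only these will be included in the statistical analysis report". The criteria are left to the SAP.
- Section 11.1.3 and the abstract: all adverse events go into the clinical study report. Neither mentions a treatment-emergent limit.
- Section 11.1.2: the detail recorded for each AE, including start time and relationship to Ayendi, depends on what the ED records hold.

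**The concern.** Ayendi is an analgesic for acute pain (section 7), and the protocol expects the indication to be an injury or trauma (section 9.4). In that population it is foreseeable that some patients have the cause of their pain confirmed, or are referred to a specialist team, after the dose. Read literally, 11.1.1 makes each of these an AE.

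The AE percentage is a secondary objective (section 8.2) of a post-authorisation safety study with at least 20 sites (section 9.2). If some sites apply the definition to the letter and others leave the injury out, the overall percentage mixes reactions after the drug with the ordinary work-up of the injury. Differences between sites then partly reflect reading habits.

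**Working it through.** **Step 1: the definitions side by side.** Take a patient whose fracture is confirmed after the dose, who is then referred and admitted, with a stay of the usual length.

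- SAE test (11.2.1): the admission is for the presenting injury and is not prolonged, so it is exempt.
- AE test (11.1.1): the fracture is a diagnosis newly entered in the notes after Ayendi, and the referral is a reason for seeing a consultant. Each limb is met, and no exemption applies.

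The same event is thus deliberately kept out of the SAE count and, on the wording, admitted to the AE count.

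**Step 2: does a later provision remove it?**

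- The time limit in 11.1.1 is tied to entry in the notes after dosing. It does not refer to onset, so an injury that pre-dates the dose can still qualify.
- The treatment-emergent rule (9.7.1) might remove it. A rule based on onset would need start times, which are recorded only if the notes have them (11.1.2). A rule based on the time of diagnosis, referral or entry would keep it. Section 9.7 requires the SAP only before database lock, so sites may transcribe AEs before the rule is settled.
- The summary by relationship (9.7.1) helps only where relationship is known. Section 11.1.1 asks the investigator to assess it, but 11.1.2 limits the CRF to what the records contain.
- The separate indication/diagnosis field (9.4) captures the injury, but nothing says that what is entered there is then not an AE.

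**Step 3: size, as an illustration only.** The protocol states no AE rate, so there is no figure to reproduce. Its general precision figure for n = 400 (section 9.5) does reproduce: 1.96 × √(0.5 × 0.5 / 400) = 0.049, or 4.9%.

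Let t be the true proportion of patients with some other AE, and s the proportion with an injury diagnosis or referral first noted after dosing that is recorded and kept. Both are assumptions, taken as independent:

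observed rate = 1 − (1 − t)(1 − s)

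| t | s = 10% | s = 50% | s = 90% |
|---|---|---|---|
| 5% | 14.5% | 52.5% | 90.5% |
| 10% | 19.0% | 55.0% | 91.0% |
| 20% | 28.0% | 60.0% | 92.0% |

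For t = 10%, s = 10%: 1 − 0.90 × 0.90 = 0.19. For t = 10%, s = 90%: 1 − 0.90 × 0.10 = 0.91. Patients counted only because of the injury would make up (0.19 − 0.10)/0.19 = 47% to (0.91 − 0.10)/0.91 = 89% of all patients with an AE. The excess of 9 to 81 percentage points exceeds the 4.9% maximum half-width, so a confidence interval would not reveal it.

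Across sites, with t = 10% everywhere and s = 50%, a literal site reports 55% and a site that leaves the injury out reports 10%.

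**Step 4: what is not affected.** Section 9.7.1 tabulates incidence by system organ class and preferred term, with each patient counted once per level. If, say, 20 of 400 patients vomit, that row reads 5% however many others have a fracture listed. The excess falls in the overall total and in the rows for the injury itself.

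**The case against.** The strongest reply is that the protocol has its own filter: only treatment-emergent AEs enter the statistical report, and a condition that pre-dates the drug is what such a rule normally removes. The SAP is not shown, and what is left to it is no defect. This stands in part: how much inflation survives cannot be known. But what a site must record as an AE is fixed in the protocol, the filter may lack the onset times it needs, and two places promise a report of all AEs.

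A second reply is that a new diagnosis, read beside the separate indication field, naturally means one other than the indication. That is a sensible reading, but not the only one, and the referral limb has no similar escape.

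Several stronger conclusions are tempting and are not supported:

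- *Every presenting injury becomes an AE.* An injury already diagnosed before the dose is not a new diagnosis after it.
- *The abstract has no time limit, so even the presenting complaint counts.* Section 11.1.1 supplies the limit, and section 9.1.1 starts the study period after administration. The abstract is merely incomplete.
- *Sedation, vomiting or respiratory depression are diluted.* Step 4 shows that their rates do not change.
- *The AE rate loses its meaning.* That would require knowing the treatment-emergent rule and how often such entries occur. The documents give neither.

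**Conclusion.** The point holds in limited form. The AE definition lacks the presenting-injury exemption that the SAE definition has, so a diagnosis of or referral for that injury first noted after dosing can be recorded as an AE. The overall AE percentage can be inflated, and inconsistently between sites.

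The size cannot be derived from the documents. The range of 19% to 91% for a true 10% rests on an assumed 10% to 90% of patients with such an entry, on independence, and on every entry surviving the treatment-emergent rule.

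The parameter is secondary and descriptive, with no formal testing planned (9.7.1). Neither primary rate nor the sample size depends on it. It should be fixed, because uneven recording may be hard to undo later, but it does not invalidate the study.

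**What to change.** 1. In 11.1.1, carry over the principle of 11.2.1: diagnosis, investigation, referral, admission or expected symptoms of the presenting injury or condition are not AEs unless there is unexpected deterioration or a suspected adverse reaction to Ayendi.
2. Put the same wording in the abstract, and add there the limit that AEs count from the administration of Ayendi.
3. Reconcile the abstract and 11.1.3 (all AEs reported) with 9.7.1 (treatment-emergent AEs only), for example by stating which set gives the headline percentage and which is only listed.

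This costs a few sentences of protocol text and matching CRF guidance, with no extra data. It is best done before data collection begins. The small downside is that sites must judge whether a new diagnosis belongs to the presenting condition, as 11.2.1 already asks of them for SAEs.
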